2.3.2 KNOWN POTENTIAL BENEFITS

The anticipated potential benefits of receiving camostat mesylate treatment for patients with COVID-19 would be reduction of viral replication, which would be presumed to accelerate the reduction of COVID-19 disease symptomatology and reduce the contagiousness of the causative virus to others.

2.3.3 ASSESSMENT OF POTENTIAL RISKS AND BENEFITS

According to what is known about COVID-19 disease and its potential for severe disease as well as transmission, and compared to the minimal risk of taking camostat mesylate, the potential benefits outweigh potential risks.

Risk of the study design itself, focused on the highly transmissible virus SARS-CoV-2 causing COVID-19 disease, mitigates risk both to subject and to study personnel during the acute phase of the study (days 0-6) and at days 14 and 28.

3 OBJECTIVES AND ENDPOINTS

OBJECTIVES	ENDPOINTS	JUSTIFICATION FOR ENDPOINTS
Primary To determine whether camostat mesylate reduces SARS-CoV-2 viral load within 2-3 days after laboratory-confirmed diagnosis of COVID-19 disease in ambulatory patients.	Primary Endpoint: 1. Change (reduction) from baseline to day 4 in respiratory (Nasopharyngeal swab, saliva RT-PCR) \log_{10} viral load .	Per FDA recommendations and our own judgment, the timing of this primary endpoint was chosen because reduction of viral load in respiratory tract samples would be expected to be associated with anti-viral activity of the study drug, and would be expected to be associated with continued reduction of viral load during drug administration, hence potential reduction severity of COVID-19 disease and reduction of transmission by reducing infectiousness of infected individual. If we are able to achieve a reduction in viral load then a trial with clinical endpoints such as risk for progression to hospitalization and/or need for intensive unit care would be justified.
Secondary 1. To determine whether camostat mesylate reduces SARS-CoV-2 viral load within 7 days after laboratory-confirmed diagnosis of COVID-19 disease in ambulatory patients.	1. Change from baseline to day 2 and to day 6 in respiratory (Nasopharyngeal swab, saliva RT-PCR) \log_{10} viral load. 2. Difference in rate of positive COVID-19 test at day 6, 14 and 28	As for the primary endpoints (above). We expect to see a time-dependent reduction of viral load, hence the second time point.

Camostat mesylate in COVID-19 Outpatients

Protocol #2000027971

Version 8.0
18 August 2020

OBJECTIVES	ENDPOINTS	JUSTIFICATION FOR ENDPOINTS
2. To determine the effect of camostat mesylate on COVID-19 symptom score. 3. To evaluate the safety of camostat mesylate 4. Adverse events	3. Change of COVID-19 symptom score from baseline, to days 6 and 14 Assessment of safety by labs and history and physical, according to The Common Terminology Criteria for Adverse Events (CTCAE) Version 5.0.	We expect to see a reduction in symptom score from baseline at day 6 and day 14 +/-. If the secondary endpoints are not achieved, then a trial to examine the effect of camostat mesylate on COVID-19 would not be justified.
Tertiary/Exploratory		
To determine clinical outcome of COVID-19 treated with camostat mesylate To determine conversion of SARS-CoV-2 antigen from positive at baseline to negative at days 6 and 14.	As an exploratory endpoint in comparing treatment to placebo groups, we will assess time to clinical improvement and risk for hospitalization. Quidel's Sofia assay will be used for antigen detection.	A tertiary objective not powered by this study. We will explore, however, whether the treatment group clinically improves or has a lower, neutral, or greater risk of hospitalization. As the Quidel assay has not been used for serial assessment of outpatients, this exploratory analysis will provide data regarding the performance of this test in our outpatient context

4 STUDY DESIGN

4.1 OVERALL DESIGN

*The scientific integrity of the trial and the credibility of the data from the trial depend substantially on the trial design. A description of the trial design should be consistent with the **Protocol Synopsis (section 1.1)** and **Protocol Schema (section 1.2)** and include:*

Hypothesis: Camostat mesylate, a serine protease inhibitor shown to inhibit SARS-CoV-2 replication *in vitro* and to reduce mortality in a mouse model of SARS, inhibits SARS-CoV-2 replication in early stage, laboratory-confirmed, ambulatory COVID-19 patients.

Trial phase: This is a phase II trial of camostat mesylate, a drug approved for clinical use in Japan for treatment of pancreatitis and postoperative reflux esophagitis.

Trial design: Randomized, double-blind, placebo-controlled clinical trial

Methods to minimize bias: Participants will be randomized equally to camostat mesylate or identical appearing placebo using a permuted-block design with variable block size. Actual treatment assignment will be concealed from the investigators and the participants.

Number of study groups/arms and study intervention duration: Two arms: **Group A, study drug (camostat mesylate); Group B, placebo.** **Duration of study: 7 days.** **Duration of involvement by participants: 28 days.**

Number of Sites: one

Name of study intervention: Camostat mesylate

Stratification: None

4.2 SCIENTIFIC RATIONALE FOR STUDY DESIGN

The rationale for placebo is that there is no known effective treatment for COVID-19 disease. The natural history of viral shedding in infected patients varies substantially among patients. Generally viral replication appears within about 5 days after exposure, and an asymptomatic phase may or may not be present for days prior to the onset of symptoms, most often described as progressive symptoms of fever, cough, malaise and shortness of breath. Because there is no available animal model in which to study the anti-SARS-CoV-2 viral effect of camostat mesylate, infected humans must be studied. Because respiratory viral burden varies substantially (orders of magnitude ranging from 10^2 - 10^9 /swab) among COVID-19-affected individuals, in order to demonstrate an antiviral effect of any drug on SARS-CoV-2, serial samples and measurement of viral load on respiratory samples must be compared between placebo and experimental groups. We will also perform viral load testing on saliva because recent studies have suggested that saliva may be more reliable; however the nasopharyngeal swab remains the gold standard. Because enrollment will be based on an initial positive COVID-19 test on a nasopharyngeal swab and participants randomized in a double-blinded way, experimental and placebo groups are expected to be comparable without bias.

4.3 JUSTIFICATION FOR DOSE

The standard dose of camostat mesylate as approved in Japan for patients with chronic pancreatitis is 600mg/day (200 mg po tid). We will increase the dose to 800mg/day (200 mg po QID) which has been shown to be safe. This choice of dosage is consistent with PK simulation data (shown above) and Ono's safety data as seen below, and the FDA IND approval letter suggested a dose of 800mg/day (200 mg po QID). The placebo control will be produced by the Yale New Haven Hospital research pharmacy to be a look-alike.

Highest dose history in clinical trials

Highest single dose

- Single oral dose of **600 mg**

No effects were observed heart rate, blood pressure and general symptoms which conducted every hour up to 4 hours after administration and 24 hours.

Highest daily dose

- Daily dose of **900 mg, p.o., t.i.d.**

Administered 900 mg/day for 8 weeks in Phase 2 study of Reflux esophagitis. Mild adverse effects were observed in 2 patients (out of total 62 patients), which were recovered soon after medication was treated.

Highly Confidential | Checked by: [redacted] | Prepared by: [redacted] | 03/18/2020

ONO PHARMACEUTICAL CO., LTD. 4/10

Incidence of adverse reactions in long-time clinical survey

Indication: Acute symptoms in chronic pancreatitis

Data collection period: January 1985 to January 1991

Average daily dose	< 300 mg	<600 mg	600mg	≥ 600mg	Unknown	Total
Patients surveyed	31	680	2605	41	26	3383
Episodes of adverse reaction	1	23	31	1	1	57
Incidence	3.2%	3.4%	1.2%	24%	3.8%	1.7%

Indication: Reflux esophagitis

Data collection period: July 1994 to June 1998

Average daily dose	< 300 mg	300mg	≥ 300mg	Unknown	Total
Patients surveyed	38	3002	137	51	3228
Episodes of adverse reaction	1	28	2	0	31
Incidence	2.6%	0.9%	1.5%	0%	1.0%

Highly Confidential | Checked by: [redacted] | Prepared by: [redacted] | 03/18/2020

ONO PHARMACEUTICAL CO., LTD. 5/10

4.4 END OF STUDY DEFINITION

A participant is considered to have completed the study if he or she has completed all phases of the study including the last visit or the last scheduled procedure shown in the Schedule of Activities (SoA), Section 1.3. The end of the study is defined as completion of the last visit or procedure shown in the SoA in the trial globally.

5 STUDY POPULATION

5.1 INCLUSION CRITERIA

Consecutive participants testing positive for COVID-19 at the Sargent Drive testing center, any other YNHHS site, or external COVID-19 testing facility will be eligible for enrollment.

In order to be eligible to participate in this study, an individual must meet all of the following criteria:

1. Be enrolled within 3 days of being notified of their first positive COVID-19 test result.
2. Evidence of a recent active COVID-19 infection, as evidenced by the positive test results being associated with at least one COVID-19-compatible symptom such as fever, upper respiratory symptoms, cough, chills, loss of taste/smell, etc.(see COVID-19-PRO symptom score sheet), or a recent high-risk exposure to COVID-19
3. Provision of informed consent
4. Stated willingness to comply with all study procedures and availability for the duration of the study
5. Male or female, aged 18 and older
6. Diagnosed with COVID-19 within past 3 days and not exhibiting manifestations requiring hospitalization such as extreme shortness of breath or severe prostration. Nurses at the study site will assess such severe conditions requiring hospitalization, which would preclude enrollment.
7. Ability to take oral medication and be willing to adhere to the camostat mesylate regimen.
8. For men and women of reproductive potential: use of condoms or other methods to ensure effective contraception with partner during study drug administration.
9. Agreement to adhere to Lifestyle Considerations (birth control measures) throughout the 7-day duration of study drug administration.
10. English and Spanish speaking subjects as well as patients speaking any language for which we can find appropriate translators will be enrolled. A short form with interpretation will be used for anyone speaking a language for which a translated informed consent form is not currently available in accordance with local site IRB policies, including developing certified translations as necessary.

5.2 EXCLUSION CRITERIA

An individual who meets any of the following criteria will be excluded from participation in this study:

1. Presence of COVID-19 disease manifestations that would require referral for consideration of hospitalization.
2. A previous positive COVID-19 test reported more than 7 days before, which would indicate likelihood of non-culturable, nonreplicating virus
3. A positive COVID-19 test without a known recent exposure that would indicate an active infection, hence an unknown chance of non-culturable, non-replicating virus being present (i.e., asymptomatic COVID-19 infection of unknown duration)
4. Known pregnancy or lactation; a positive urine pregnancy test done at the enrollment (day 0 visit) for women with child bearing potential.
5. Known allergic reactions to components of camostat mesylate.

With regard to inclusion or exclusion of women of child-bearing potential, women who tell us they know they are pregnant are excluded. All women of child-bearing potential who test positive for pregnancy by urine test at first visit are excluded. A day 14 followup blood pregnancy test will be done on appropriate enrolled women (i.e. those who had a negative urine pregnancy test on day 0 for further safety assessment.

5.3 LIFESTYLE CONSIDERATIONS

Female subjects with potential for childbearing will be asked to maintain at least two forms of birth control during the 7 days of study drug/placebo administration, including but not limited to abstinence from sexual intercourse, condom use and/or using oral contraceptives.

During this study, participants are asked to comply with State public health requirements and the U.S. Centers for Disease Control and Prevention in terms of social distancing and discontinuing home isolation (<https://www.cdc.gov/coronavirus/2019-ncov/hcp/disposition-in-home-patients.html>), which will be provided in written form to participants.

5.4 SCREEN FAILURES

The study design is expected to minimize screen failures because enrollment will be based on consecutively diagnosed COVID-19+ individuals. Screen failures are defined as participants who consent to participate in the clinical trial but are not subsequently randomly assigned to the study intervention or entered in the study. A minimal set of screen failure information is required to ensure transparent reporting of screen failure participants, to meet the Consolidated Standards of Reporting Trials (CONSORT) publishing requirements and to respond to queries from regulatory authorities. Minimal information includes demography, screen failure details, eligibility criteria, and any serious adverse event (SAE).

5.5 STRATEGIES FOR RECRUITMENT AND RETENTION

Special circumstances must prevail for recruitment and retention in this study given the contagiousness potential of COVID-19.

Target study sample size: 114, with no pre-specified breakdown by gender, race, ethnicity, or age;

Anticipated accrual rate: 1-5 participants weekly, may take longer

Anticipated number of sites: one, Yale School of Medicine/Yale New Haven Health, New Haven, CT

Source of participants: Persons with a positive SARS-CoV-2 test recorded at the clinical site, referral from healthcare personnel due to a positive SARS-CoV-2 test, or self-referral after receiving a positive SARS-CoV-2 test.

How potential participants will be identified and approached: Participants who are diagnosed within the YNHH Health System will be identified via a daily JDAT data output that will identify new COVID-19 outpatients who have not opted out of being contacted for Yale research studies. Approved study personnel will use this list to identify subjects that fulfill inclusion criteria and are not excluded according to exclusion criteria, and then contact potential subjects to ask if they might be willing to participate in the study. If so, the study will be explained and the informed consent process initiated.

Alternatively, physicians/APRNs/HCWs may refer a potential participant based on a new positive COVID-19 test, or patients may self-refer themselves for potential participation.

Participants will be offered compensation . Free parking or reimbursement for parking will be provided for outpatient visits. Study site staff will make efforts to arrange and pay for safe transportation to and from the study site if a participant meeting eligibility criteria otherwise cannot make their appointments.

6 STUDY INTERVENTION

6.1 STUDY INTERVENTION(S) ADMINISTRATION

6.1.1 STUDY INTERVENTION DESCRIPTION

Study intervention: camostat mesylate 200mg po qid vs. placebo. Commercially available in Japan, but not in the United States.

6.1.2 DOSING AND ADMINISTRATION

Camostat mesylate 200 mg po qid vs. placebo for 7 days.

Two days of study drug or placebo will be provided every other day in the study clinic at the time of check-in, prior to being swabbed and obtaining saliva samples.

6.2 PREPARATION/HANDLING/STORAGE/ACCOUNTABILITY

6.2.1 ACQUISITION AND ACCOUNTABILITY

Ono Pharmaceutical, Japan, will provide Camostat mesylate 100 mg tablets as FOIPAN. The Yale New Haven Hospital research pharmacy will receive and store the drug within 15-30°C range according to protocol storage requirements.

Microcrystalline Cellulose NF (PH-102) for placebo formulation will be acquired from Fagron.

Empty gelatin capsules Size 0, for over-encapsulation will be acquired from Fagron.

Before Ono Pharmaceutical can send the drug, an IND will be obtained from the FDA.

The Sponsor-Investigator and the Yale New Haven Hospital research pharmacy will keep accountability records for all investigational products acquired, dispensed, used and disposed.

6.2.2 FORMULATION, APPEARANCE, PACKAGING, AND LABELING

[figure not shown]
Camostat mesylate will be provided by Ono Pharmaceuticals as 500 tablets/bottle in glass bottles. Each tablet contains 100 mg of Camostat mesylate. For study administration two tablets will be combined (by investigational pharmacy) into one 200 mg capsule (see page 23) and subjects will take one capsule qid of either study drug or placebo. Placebo will be formulated to be similar in appearance to the study drug and provided in similar plastic containers.

Chemical name: 4-[[4-[(Aminoiminomethyl)amino]benzoyl]oxy]benzeneacetic acid 2-(dimethylamino)-2-oxoethyl ester methanesulfonate.

International Nonproprietary Name (INN): Camostat

Molecular formula: $C_{20}H_{22}N_4O_5 \cdot CH_4O_3S$

Molecular weight: 494.52

Structural formula

6.2.3 PRODUCT STORAGE AND STABILITY

The study drug Camostat is stable at 25°C and should be kept at ambient (15-30°C) temperature for long term storage. For short term storage (up to 30 days) to facilitate daily dispensing of the drug it will be kept at ambient office or clinic temperature.

Placebo for Camostat will also be stored at ambient (15-30°C) temperature for long term storage. For short term storage (up to 30 days) to facilitate daily dispensing of the drug it will be kept at ambient office or clinic temperature.

Drug will be stored in locked cabinets at ambient (15-30°C) temperature at all times other than during active dispensing.

6.2.4 PREPARATION**Encapsulated Camostat 200 mg Capsules**

For blinding, two intact active camostat 100 mg tablets will be placed in a capsule shell, back filled with sufficient quantity of microcrystalline cellulose, and closed. The capsules are visually inspected and packed into polypropylene bottles.

Placebo for Encapsulated Camostat 200 mg dose Capsules

Matching placebo will be compounded, using a matching empty capsule filled with sufficient quantity of microcrystalline cellulose. The capsules are visually inspected and packed into polypropylene bottles.

Assigned beyond use date is not later than the time remaining until the earliest expiration date of any ingredient or 6 months.

Master formulation record and compounding record will be kept for the compounding.

Compounding, packaging and labelling will be carried out by Investigational Drug Service Pharmacy, Yale-New Haven Hospital.

Labeling:

Camostat 200 mg dose Capsules (Active)

Compounding Date:

Lot:

Exp Date:

Qty:

Protocol #

Storage Condition (Room Temp 15-30°C)

"Caution: New Drug--Limited by Federal (or United States) law to investigational use."

Placebo for Camostat 200 mg Capsules

Compounding Date:

Lot:

Exp Date:

Qty:

Protocol #

Storage Condition (Room Temp 15-30 °C)

"Caution: New Drug--Limited by Federal (or United States) law to investigational use."

Dispensing:

For dispensing, 8 capsules of overencapsulated Camostat 200 mg per capsule or identically appearing Placebo for camostat mesylate 200 mg will be packaged in a polypropylene bottle and given to enrolled research participants every other day. The bottles will be labeled with dispensing label containing patient name, administration instructions, and provider information per state pharmacy regulations.

6.3 MEASURES TO MINIMIZE BIAS: RANDOMIZATION AND BLINDING

Consecutive consenting COVID-19+ patients will be recruited as participants, who will be randomized equally to camostat mesylate or placebo using a permuted-block design with variable block size. Actual treatment assignment will be double-blind, concealed from the investigators and the participants. The YCCI statistical group (YCAS) will generate the randomization scheme and provide it to the pharmacy. Research pharmacy staff will prepare study drug and placebo for dispensing and assign and record which subject are assigned to receive them. The study site team will record what each participant receives according to assigned kit #.

6.4 STUDY INTERVENTION COMPLIANCE

The study design is built around obtaining respiratory swabs and saliva from participants. To encourage compliance with study protocol, study drug/placebo will be provided every other day (prior to swabbing and saliva collection) and verbal assessment of whether study drug/placebo was taken as prescribed will be done.

Participants will have the option of not being swabbed again or providing saliva, even after receiving study drug, but lack of day 0 and 4 NP swabs would be a protocol deviation although they would be retained in intention to treat analysis. NP swabs are required at days 0, 4, 14, 28; optional swabs at days 2 and 6. Saliva will be collected at all study visits.

6.5 CONCOMITANT THERAPY

Medications to be reported in the Case Report Form (CRF) are concomitant prescription medications (oral and parenteral), over-the-counter medications and supplements. There are no restrictions. We will track all concomitant medications that subjects take.

6.5.1 RESCUE MEDICINE

Not applicable

7 STUDY INTERVENTION DISCONTINUATION AND PARTICIPANT DISCONTINUATION/WITHDRAWAL

7.1 DISCONTINUATION OF STUDY INTERVENTION

Reasons why a study subjects may be withdrawn from the study intervention include, but are not limited to:

- Subject request (withdrawal of consent)
- Protocol violation, i.e. declining to take drug or be swabbed or providing saliva for viral load two times.
- AE or reactions
- Any condition, interaction, or contraindication where continued participation in the study will result in an unacceptable risk for the subject, as assessed by the Investigators or advisers
- Discontinuation of the study by the Sponsor
- Lost to follow-up

7.2 PARTICIPANT DISCONTINUATION/WITHDRAWAL FROM THE STUDY

Participants are free to withdraw from participation in the study at any time upon request. An investigator may discontinue or withdraw a participant from the study for the following reasons:

- Pregnancy
- Significant study intervention non-compliance
- If any clinical adverse event (AE) or other medical condition or situation occurs such that continued participation in the study would not be in the best interest of the participant
- Disease progression which requires discontinuation of the study intervention
- If the participant meets an exclusion criterion (either newly developed or not previously recognized) that precludes further study participation
- Participant unable to receive study intervention
- The reason for participant discontinuation or withdrawal from the study will be recorded on the Case Report Form (CRF). Subjects who provide informed consent and are randomized but do not receive the study intervention may be replaced. Subjects who sign the informed consent form, and are randomized and receive the study intervention, and subsequently withdraw, or are withdrawn or discontinued from the study will be replaced.

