1.3 SCHEDULE OF ACTIVITIES (SOA)

Procedures	Enrollment, Study Visit 1, Day 0	Study Visit 2 Day 2	Study Visit 3 Day 4	Study Visit 4 Day 6	Study Visit 5 Day 14+/- 2 days	Study Visit 6 Day 28+/- 2 days
Informed consent	X					
Demographics	X					
Medical history	X					
Randomization	X					
Administer study intervention: Subjects receive two days worth of drug/placebo on days 0, 2, 4 and one day of drug/placebo on day 6	X Drug/placebo For 2 days	X Drug/placebo For 2 days	X Drug/placebo For 2 days	X Drug/placebo For 1 day		
Nasopharyngeal swabs, saliva for COVID-19 RT-PCR and antigen testing	X	X Swabs optional	X	X Swabs optional	X	X
Physical exam: Vital signs, wt, pulse oximetry, other as clinically indicated	X	X	X	X	X	X
Urine pregnancy test (as indicated)	X					
Blood pregnancy test (as indicated)					X	
Hematology and coagulation	X				X	X
Blood chemistries	X				X	X
Adverse event review and evaluation	X	X	X	X	X	X
Concomitant medication review	X	X	X	X	X	X
Blood for research biorepository	X				X	X
Complete Case Report Forms (CRFs)	X	X	X	X	X	X

All subjects, regardless of study arm (blinded to subjects and investigators), will be tracked for their health status through daily phone calls from days 0 to day 14 with routine, scheduled daily phone calls by study staff to help participants fill out symptom scores on the standardized COVID-19-PRO instrument. Any subject reporting concerning symptoms, particularly chest pain, shortness of breath, extreme prostration, change in mental status will be referred to for emergency care. Subjects will be given a contact phone number of PI or designee to contact for any concerns. If there is complete resolution of symptoms at the day 14 visit, then phone calls will not be routinely continued by our study staff but subjects will be encouraged to call PI or designee for concerns or discussions.

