7.3 LOST TO FOLLOW-UP

A participant will be considered lost to follow-up if he or she fails to return for two or more visits and is unable to be contacted by the study site staff; if a subject is hospitalized outside the YNHHS we will attempt follow for clinical outcomes and concomitant medications.

The following actions must be taken if a participant fails to return to the clinic for a required study visit:

- The site will attempt to contact the participant and reschedule the missed visit within one day and counsel the participant on the importance of maintaining the assigned visit schedule and ascertain if the participant wishes to and/or should continue in the study.
- Before a participant is deemed lost to follow-up, the investigator or designee will make every effort to regain contact with the participant (where possible, 3 telephone calls and, if necessary, a certified letter to the participant's last known mailing address or local equivalent methods). These contact attempts should be documented in the participant's medical record or study file.
- Should the participant continue to be unreachable, he or she will be considered to have withdrawn from the study with a primary reason of lost to follow-up.

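### The day-4 ITT ANCOVA names no primary handling of missing values, and section 7.2 lets drug-level events end study participation with no provision to keep sampling to day 4

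*Combined protocol and SAP*

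**What the plan says.** **Analysis.** Section 9.4.2 specifies ANCOVA on the day-4 change, adjusted for baseline, by intention to treat. On missing data it commits to assessing the mechanism and the impact. Analyses under missing-at-random (MAR) or not-at-random assumptions are sensitivity analyses that will be considered as appropriate. Section 9.3 defines ITT by assigned treatment only. Section 6.4 lets participants decline swabs or saliva after receiving drug, calls missing day-0 and day-4 NP swabs a deviation, and still keeps these people in ITT.

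**Leaving the study.** Section 7.1 covers stopping drug; section 7.2 covers leaving the study. Three of the reasons in 7.2 for which an investigator may withdraw someone from the study concern the drug: "Significant study intervention non-compliance", "Participant unable to receive study intervention" and "Disease progression which requires discontinuation of the study intervention". Dosed participants who are "randomized and receive the study intervention, and subsequently withdraw, or are withdrawn or discontinued from the study will be replaced". Under section 7.3, a participant who stays unreachable is handled in the same way: "he or she will be considered to have withdrawn from the study with a primary reason of lost to follow-up".

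**Provisions that limit loss.** Sections 1.3 and 8.1 schedule day-4 NP and saliva samples without reference to drug intake. Section 7.3 says "The site will attempt to contact the participant and reschedule the missed visit within one day" and "if a subject is hospitalized outside the YNHHS we will attempt follow for clinical outcomes and concomitant medications". Under section 1.3, all subjects "will be tracked for their health status through daily phone calls from days 0 to day 14". Section 8.3.9 allows other follow-up to continue after a pregnancy stops drug.

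**The concern.** A single-timepoint ANCOVA cannot use a record that lacks the baseline or day-4 value of the analysed specimen. Keeping such a person in ITT therefore has no effect on the primary result unless a rule supplies a value, and no rule is named.

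Section 7.2 can add to the gap. Progression, intolerance and non-adherence may be related to viral load or to treatment arm, so loss for these reasons cannot be presumed random. If it is related to the day-4 outcome and differs by arm, the observed-case contrast is biased, in either direction. A method chosen after the data are seen would add an avoidable degree of freedom to the result that, under section 2.1, decides whether the drug is pursued.

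**Working it through.** **1. The plan's own figure.** Inputs from section 9.2: changes of 4 and 1 log10, SD 5.0, two-sided 10%, power 90%, R-squared 0.
- Difference: (4 - 1)/5.0 = 0.6 SD, which is the stated effect size of 0.3 on the ANCOVA scale.
- ANCOVA power (noncentral F, one covariate): 89.85% at 96 and 90.4% at 98. The 98 reproduces.
- 49 x 1.15 = 56.35, rounded up to 57 per arm, or 114. The sample-size arithmetic is not at fault.

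**2. Does any passage keep day-4 sampling going after a drug-level withdrawal?**
- The schedule sets visits for participants in the study; it does not address someone withdrawn from it.
- Rescheduling in 7.3 applies to a missed visit.
- The hospitalisation clause in 7.3 covers clinical outcomes and medications, not viral load.
- The daily calls collect health status and symptom scores, not respiratory samples.
- Section 8.3.9 is permissive and covers pregnancy only.

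So no passage does.

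**3. Bias of the observed-case contrast.** Let p be the proportion lost by day 4 in an arm and D the gap, after baseline adjustment, between those observed and those lost. Then

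bias = p1 x D1 - p2 x D2.

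Both p and D are assumptions. The documents give only a 10% overall loss allowance (section 9.2).
- 10% v 0%, D = 1 to 3 log10: 0.10 x 1 = 0.1 to 0.10 x 3 = 0.3 log10. Dividing by 5.0 gives 0.02 to 0.06 SD.
- 10% v 5%, D = 1 log10 in both arms: 0.10 - 0.05 = 0.05 log10, or 0.01 SD.
- Equal loss and equal gap: 0.

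**4. Effect on error and power.** Two looks at half and full information, boundary 1.875 at each (sections 9.4.2 and 9.4.6), bivariate normal with correlation 0.707. With 57 v 57 x 0.90 = 51.3 evaluable, the standard error is sqrt(1/57 + 1/51.3) = 0.192 SD. Bias b shifts the final statistic by b/0.192 (0.104 at 0.02 SD, 0.312 at 0.06 SD) and the interim statistic by 0.707 times that.

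| Loss | Gap (log10) | Bias (SD) | Upper-side error, bias towards drug | Power at 0.6 SD, bias against drug |
|---|---|---|---|---|
| 10% v 0% | none | 0 | 5.0% | 90.6% |
| 10% v 0% | 1 | 0.02 | 6.0% | 88.8% |
| 10% v 0% | 3 | 0.06 | 8.6% | 84.4% |
| 10% v 5% | 1 | 0.01 | 5.5% | 89.0% (90.0% without bias) |

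The last row uses 57 x 0.95 = 54.15 v 51.3 evaluable.

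**5. What an MAR model recovers.** Simulation with 10% lost, loss depending on the day-4 value itself, and imputation by regression on day 2. At assumed day-2/day-4 residual correlations of 0.3, 0.5 and 0.7, it removes about 9%, 25% and 48% of the bias, and about half of that if only half of the leavers have a day-2 value.

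**6. Replacement and the interim trigger.** If replacements count within the target, 114 are randomised. If leavers are replaced until 114 remain, 114/0.90 = 126.7, about 127, at 10% loss. A look at 57 of 127 changes upper-side error from 5.0% to 5.1%. Two-look power is 91.9% with 114 evaluable and 89.2% if 10% are lost in each arm without replacement.

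**The case against.** Much of this is partly covered. Section 9.4.2 is not silent: it commits to assessing the missingness and mentions sensitivity analyses. Stopping drug and leaving the study are separate sections, and withdrawal under 7.2 is discretionary. The trial is double-blind, the day-4 visit comes early, missed visits are chased, and the safety data in section 2.2 show few adverse reactions (1.3%-1.8%). Loss of 10% in one arm and none in the other by day 4 is thus a pessimistic pattern. Observed-case ANCOVA is unbiased if missingness depends only on arm and baseline, and an MAR model removes only part of the bias when it does not. All of this stands and limits the size. It does not supply a primary rule or a statement that sampling continues.

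Three stronger readings are tempting, and the documents do not support them.
- *Replacement biases the trial or inflates type I error.* By itself it does neither. No passage removes replaced participants from ITT, and section 9.3 reads as keeping them by assignment. Counting replacements within the 114 is also a consistent reading.
- *The two wordings of the interim trigger (half enrolled in 9.2, half with the endpoint in 9.4.6) matter for error.* The effect is negligible.
- *Error could reach about 12%.* That needs a bias of 0.10 SD, for example 10% one-sided loss with a gap of 1 SD. On the planning SD this gap is 5 log10, against a range of 10^2 to 10^9 per swab in section 4.2.

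**Conclusion.** The concern holds for the primary analysis and for data collection after drug stops. As written, the ITT ANCOVA is observed-case, and section 7.2 can discard day-4 values that it needs. Under the assumptions shown the damage is modest: 0.05-0.3 log10 of bias, upper-side error of about 5.5%-8.6% instead of 5.0%, or a power loss of about 1 to 6 percentage points.

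The size rests on assumed loss rates and leaver gaps, and on the SD of 5.0, which section 9.2 offers as one scenario. With a smaller true SD, the same log10 gap would be a larger bias in SD units. The direction is unknown.

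The plan should be changed because the remedy is cheap and uses samples already scheduled, not because a large bias has been shown. The number of replacements and the interim trigger are matters of wording only.

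**What to change.** 1. Reconcile sections 6.4, 7.1 and 7.2 so that stopping study drug does not by itself end data collection. Still seek the day-4 NP and saliva samples and later outcomes at the existing visits and calls, unless consent is withdrawn or the investigator judges further study procedures not to be in the participant's best interest. This concerns data collection only, not when drug stops.
2. State that every randomised participant is in the ITT set. Make the primary analysis either a baseline-adjusted longitudinal model with a day-4 contrast, or multiple imputation using the day 0, 2 and 6 values including saliva. Keep observed-case ANCOVA as a sensitivity analysis.
3. Because an MAR model recovers only part of the bias, fix one not-at-random sensitivity analysis before the data are seen. State the shifts in log10, for example 1, 2 and 3, and apply them to each arm separately.
4. Wording only: say whether replacements count within the 114, and align the interim trigger in 9.2 and 9.4.6.

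The cost is revised text, slightly more analysis work and some effort to sample people who have stopped drug. Sampling may not be possible for those in hospital.
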